3. Overactive Bladder Questionnaire- subscales (OAB-q) – The OAB-q is a validated, responsive questionnaire that includes 8 symptom bother items (SS) and 25 health related quality of life (HRQOL) items of 4 subscales (coping, concern, sleep, and social interaction).⁷⁶ In a systematic review of UI questionnaires by Avery et al, the OAB-q was rated as “grade A”, highest recommendation specifically for OAB symptoms.⁷⁷ Each item is rated on a 6-point Likert scale ranging from “not at all bothered” to “a very great deal bothered” for symptom items and “none of the time” to “all of the time” for HRQOL items. Subscales are summed and transformed into scores ranging from 0-100 with higher bother scores indicating increasing symptom bother and higher HRQOL scores indicating better quality of life.^{78,79} We will compare change from baseline in OAB-q subscale scores at 3 and 6 months between treatment groups.

3.4.3.b **Quality of Life/Global Impression**

We will compare change from baseline score in the measures below at 3 and 6 months between treatment groups.

1. Incontinence Impact Questionnaire Long Form (IIQ-LF)⁵⁷
2. Pelvic Organ Prolapse/Urinary Incontinence Sexual Questionnaire (PISQ-IR)⁸⁰
3. European Quality of Life-5 Dimensions (EQ-5D)⁸⁴
4. Short Form 36 (SF-36)⁸¹ and Short Form 6D (SG-6D)⁸²
5. Patient Global Impression of Improvement (PGI-I) and Patient Global Impression of Severity (PGI-S).⁸³ Observed PGI-I at 3 and 6 months will be compared between groups.

3.4.3.c **Safety/Additional Treatment**

1. Additional re-treatments for SUI or UUI within 6 months of treatment, and type of re-treatment
2. Return to OR for sling revision due to worsened OAB symptoms, urinary retention, mesh exposure, repeat sling
3. Rate of urinary retention, UTIs and recurrent UTIs
4. Rate of other serious and non-serious adverse events.

3.4.3.d Cost-Effectiveness Outcomes

The cost-effectiveness analysis will be conducted from the health care sector and societal perspectives and will be expressed as incremental cost required to produce one additional unit of quality-adjusted life year (QALY). Data on each subject's use of medical and non-medical resources, related to urinary incontinence will be collected during the follow up period. Direct and indirect costs of the treatment of urinary incontinence with Botox A compared to mid-urethral sling (MUS) and women's preference for health states for improvement in urinary incontinence will be estimated.

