8.3 Demographic and Baseline Characteristics

Demographic and baseline clinical characteristics for the study participants will be summarized by study arm using the general analysis rules describe above. Variables of interest include age (years), parity, gravidity, race and ethnicity, BMI, education level (classified as binary variable as having some education greater than high school), smoking status (current yes or no), menopausal status, and estrogen use. Also included is time from baseline to treatment and percent of participants with > 91 days to treatment.

Baseline levels of all OAB and QOL measures will be presented on efficacy tables.

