Change from Baseline OAB- q HRQL Coping Score at 3, 6, 9, 12 Months	Continuous	The OAB-q HRQL Coping Score will be computed at baseline and 6 months (and 3, 9, and 12 months) using the standard scoring algorithm. Specifically, instructions are to sum responses across questions 9, 11, 16, 21, 22, 26, 32, and 33 (1= None of the time, 2=A little bit of the time, 3=Some of the time, 4=A good bit of the time, 5=Most of the time, 6=All of the time), then subtract from the maximum possible score (48) and divide by the range of possible score (48-8=40), then multiply by 100. If less than half of the responses are missing, then the score will be calculated by substituting the missing responses with the average of the non-missing responses, otherwise no score is calculated. The outcome will then be computed as the difference in score at 6 months				

Variable	Туре	Definition			
		(and 3, 9, and 12 months) and the score at baseline. If data for an assessment time point are missing, the outcome variable will be coded as missing.			
Change from Baseline OAB- q HRQL Concern Score at 3, 6, 9, 12 Months	Continuous	The OAB-q HRQL Concern Score will be computed at baseline and 6 months (and 3, 9, and 12 months) using the standard scoring algorithm. Specifically, instructions are to sum responses across questions 12, 13, 14, 19, 23, 25, and 29 (1= None of the time, 2=A little bit of the time, 3=Some of the time, 4=A good bit of the time, 5=Most of the time, 6=All of the time), then subtract from the maximum possible score (35) and divide by the range of possible score (42-7=35), then multiply by 100. If less than half of the responses are missing, then the score will be calculated by substituting the missing responses with the average of the non-missing responses, otherwise no score is calculated. The outcome will then be computed as the difference in score at 6 months (and 3, 9, and 12 months) and the score at baseline. If data for an assessment time point are missing, the outcome variable will be coded as missing.			

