Change from Baseline OAB- q HRQL Sleep Score at 3, 6, 9, 12 Months	Continuous	The OAB-q HRQL Sleep Score will be computed at baseline and 6 months (and 3, 9, and 12 months) using the standard scoring algorithm. Specifically, instructions are to sum responses across questions 10, 15, 17, 24, and 30 (1= None of the time, 2=A little bit of the time, 3=Some of the time, 4=A good bit of the time, 5=Most of the time, 6=All of the time), then subtract from the maximum possible score (30) and divide by the range of possible score (30-5=25), then multiply by 100. If less than half of the responses with the average of the non-missing responses, otherwise no score is calculated. The outcome will then be computed as the difference in score at 6 months (and 3, 9, and 12 months) and the score at baseline. If data for an assessment time point are missing, the outcome variable will be coded as missing.			
Change from Baseline OAB- q HRQL Social Score at 3, 6, 9, 12 Months	Continuous	The OAB-q HRQL Social Score will be computed at baseline and 6 months (and 3, 9, and 12 months) using the standard scoring algorithm. Specifically, instructions are to sum responses across questions 18, 20, 27, 28, and 31 (1= None of the time, 2=A little bit of the time, 3=Some of the time, 4=A good bit of the time, 5=Most of the time, 6=All of			

Variable	Type Definition				
		the time), then subtract from the maximum possible score (30) and divide by the range of possible score (30-5=25), then multiply by 100. If less than half of the responses are missing, then the score will be calculated by substituting the missing responses with the average of the non-missing responses, otherwise no score is calculated. The outcome will then be computed as the difference in score at 6 months (and 3, 9, and 12 months) and the score at baseline. If data for an assessment time point are missing, the outcome variable will be coded as missing.			

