Change from Baseline OAB- q HRQL Total Score at 3, 6, 9, 12 Months		The OAB-q HRQL Total Score will be computed at baseline and 6 months (and 3, 9, and 12 months) using the standard scoring algorithm. Specifically, instructions are to sum the OAB-q HRQL Coping, Concern, Sleep, and Social prior to subtracting from the respective maximum possible scores, then subtract from the maximum possible sum score (150) and divide by the range of possible scores ((18+42+30+10=150)-(8+7+5+5=25)=125), then multiply by 100. The outcome will then be computed as the difference in score at 6 months (and 3, 9, and 12 months) and the score at baseline. If any of the listed subscales are missing, the Total score will also be set to missing. If data for an assessment time point are missing, the outcome variable will be coded as missing.			
OAB-SAT-q Satisfaction Score at 3, 6, 9, 12 Months	Continuous	 NOTE: The scoring manual for the OAB-SAT-q states that higher scores should correspond to better outcomes and details that final composite scores for each dimension should be obtained by subtracting raw scores from the highest possible score and dividing by range. However, based on the direction of score for individual responses, this derivation would result in lower scores corresponding with better outcomes. We have adjusted the scoring algorithm instead to be: 100*(raw score – lowest possible score)/score range. This calculation results in higher scores corresponding to better outcomes and an overall scale of 0-100. The OAB-SAT-q Satisfaction Score will be computed at 6 months (and 3, 9, and 12 months) using the standard scoring algorithm. Specifically, instructions are to sum responses across questions 1, 2, and 3 (1=Extremely Dissatisfied,, 6=Extremely Satisfied), then subtract the lowest possible score (3) from the raw score and divide by the range of possible scores (18-3=15), then multiply by 100. If less than half of the 			

Variable	Туре	Definition				
		responses are missing, then the score will be calculated by substituting the missing responses with the average of the non-missing responses, otherwise no score is calculated. If data for an assessment time point are missing, the outcome variable will be coded as missing.				

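### SAP 9.2 gives the OAB-q Concern maximum as 35 where the items give 42; programmed as written, the baseline Concern levels would be 20 points too low

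*SAP*

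**What the plan says.** The Concern row of SAP 9.2 tells the programmer to "sum responses across questions 12, 13, 14, 19, 23, 25, and 29", with responses coded "1= None of the time, 2=A little bit of the time, 3=Some of the time, 4=A good bit of the time, 5=Most of the time" and 6 for the highest category. It then says to "subtract from the maximum possible score (35) and divide by the range of possible score (42-7=35", and to multiply by 100.

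The sister subscales use the same template. Coping, with eight items, says to "subtract from the maximum possible score (48) and divide by the range of possible score (48-8=40". Sleep, with five items, says to "subtract from the maximum possible score (30) and divide by the range of possible score (30-5=25", and Social, also five items, has the same figures as Sleep.

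The HRQL Total is built from the four raw sums, combined "prior to subtracting from the respective maximum possible scores, then subtract from the maximum possible sum score (150", and is divided by a range of 125. The Concern component printed inside that total is 42.

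Protocol 3.4.3.a describes the intended scale: "Subscales are summed and transformed into scores ranging from 0-100", with higher HRQOL scores meaning better quality of life. SAP 8.3 adds that "Baseline levels of all OAB and QOL measures will be presented on efficacy tables". The analysed Concern outcome is the change from baseline at 3, 6, 9 and 12 months.

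**The concern.** One sentence uses two different maxima for the same raw sum: 42 in the range and 35 in the subtraction. Only one can be right, and the 35 equals the range. With 35, the formula cannot produce the 0 to 100 scale in the protocol, and it gives negative scores to the women with the worst responses.

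At stake is how the presented Concern levels read. The baseline Concern mean would stand 20 points below its true value, next to correctly scaled Coping, Sleep and Social means. A reader could take this to mean that concern is much more impaired than the other domains at entry. Comparison with baseline Concern levels in other trials would fail for the same reason.

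**Working it through.** **Inputs, all from SAP 9.2.** Items per subscale: Coping 8, Concern 7, Sleep 5, Social 5. Each item is scored 1 to 6. Write *n* for the number of items, so the raw sum runs from *n* to 6*n*. The score is 100 × (maximum − raw) / range.

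**Step 1. Reproduce the stated maxima and ranges.**

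| Subscale | Items | True maximum (6*n*) | True range (5*n*) | Stated maximum | Stated range |
|---|---|---|---|---|---|
| Coping | 8 | 48 | 40 | 48 | 40 |
| Concern | 7 | 42 | 35 | **35** | 35 |
| Sleep | 5 | 30 | 25 | 30 | 25 |
| Social | 5 | 30 | 25 | 30 | 25 |

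Seven of the eight stated figures reproduce. Only the Concern maximum does not.

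**Step 2. The Concern scale as written and as corrected.**

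- As written, best response (raw 7): 100 × (35 − 7)/35 = 80.
- As written, worst response (raw 42): 100 × (35 − 42)/35 = −20.
- With 42, best response: 100 × (42 − 7)/35 = 100.
- With 42, worst response: 100 × (42 − 42)/35 = 0.
- The difference at any raw sum is 100 × (42 − 35)/35 = 20 points.
- As written, the score is negative for raw sums 36 to 42, that is, for a mean item response above 35/7 = 5.

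The missing-item rule fills gaps with the mean of the answered items. The raw sum therefore stays between 7 and 42, and the 20-point offset is unchanged.

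**Step 3. Change from baseline.** With baseline raw sum *b*, follow-up raw sum *f* and any maximum *M*:

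100 × (*M* − *f*)/35 − 100 × (*M* − *b*)/35 = 100 × (*b* − *f*)/35.

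*M* drops out. Over every pair of raw sums from 7 to 42, the two versions differ by 0.

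**Step 4. The model with baseline as covariate.** Lowering every baseline value by 20 changes only the intercept, by 20 times the baseline slope. In a check on made-up data (138 women, two equal arms, change regressed on arm and baseline), the treatment coefficient was 3.658 with either maximum, and the baseline slope was −0.126 with either. The intercept was 21.47 with 35 and 23.99 with 42. The gap of 2.52 equals 20 × 0.126. The baseline mean was 27.5 with 35 and 47.5 with 42.

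**Step 5. HRQL Total.** The item counts give a maximum of 48 + 42 + 30 + 30 = 150 and a minimum of 8 + 7 + 5 + 5 = 25, so the range is 125. The SAP uses 150 and 125. Both are right, and both take 42 for Concern. The total starts from raw sums, so the 35 never enters it.

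**The case against.** The strongest reply is that this is a slip of the pen with no established effect on any result. The correct maximum stands in the same sentence and again in the HRQL Total row. The row invokes the standard scoring algorithm, and the protocol fixes the scale at 0 to 100. A programmer had 42 to hand, and negative values would be conspicuous. The documents contain no code and no results. This stands: the error in the text is certain, and the error in the output is conditional.

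Three stronger readings are tempting, and the documents do not support them.

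- **A reader might infer that every Concern level reported at every visit is 20 points low.** That assumes the code follows the text. It also goes beyond the levels promised: SAP 8.3 commits to baseline levels only, the analysed outcome is the change, and the over-time figure listed in SAP 15 covers primary and secondary measures, whereas SAP 3.2.3 lists the OAB-q as exploratory.
- **A reader might infer that the comparison between arms is distorted.** Steps 3 and 4 of the working show that it is not.
- **A reader might infer that the HRQL Total is also wrong**, because its maximum is printed as 18+42+30+10=150 and those four numbers add to 100. The 18 and 10 may be misread digits for 48 and 30 from the conversion of the PDF to text. The formula uses only 150 and 125, which are correct, so this is at most a print check.

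What the reply does not remove is that SAP 9.2 is the scoring specification. If it was followed, a presented table is wrong. If it was not, the specification misdescribes what was done.

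**Conclusion.** The Concern maximum in SAP 9.2 is wrong: it should be 42, and 35 is the range. On the assumption that the formula is programmed as written, Concern runs from −20 to 80, and the baseline Concern levels in the efficacy tables would be exactly 20 points too low on a scale meant to run from 0 to 100, and out of line with the other three subscales.

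The reach is narrow. It covers the levels of one subscale of one exploratory instrument. Concern change scores, their treatment differences, confidence intervals and p-values do not move, and neither does the HRQL Total. The UDI outcomes are not touched. This is a correction of low severity, worth making because it is certain and costs almost nothing.

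**What to change.** In the Concern row of SAP 9.2, replace the maximum of 35 with 42, so that the score is 100 × (42 − raw)/35. Then check that the scoring program uses 42. A quick test is that no Concern score falls below 0 and that a woman answering 1 to all seven items scores 100. The code check matters more than the edit: changing the text does not repair a table if the program used 35.

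While the row is open, compare the sum in the HRQL Total row with the source file and confirm that it prints 48+42+30+30=150. No calculation depends on it.

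The cost is one number in the SAP and one check of the code. If the program did use 35, the baseline Concern levels need re-running, but no model of change does.

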OAB-SAT-q Side Effects Score at 3, 6, 9, 12 Months	Continuous	NOTE: The scoring manual for the OAB-SAT-q states that higher scores should correspond to better outcomes and details that final composite scores for each dimension should be obtained by subtracting raw scores from the highest possible score and dividing by range. However, based on the direction of score for individual responses, this derivation would result in lower scores corresponding with better outcomes. We have adjusted the scoring algorithm instead to be: 100*(raw score – lowest possible score)/score range. This calculation results in higher scores corresponding to better outcomes and an overall scale of 0-100.				
		The OAB-SAT-q Side Effects Score will be computed at 6 months (and 3, 9, and 12 months) using the standard scoring algorithm. Specifically, if the response to question 5 is Never then the score is 100, regardless of the responses to questions 6 and 7. If the response to question 5 is not Never, then sum the responses across questions 5 (reverse coded: 1=All of the time,, 5=A little of the time), 6 (1=Extremely bothersome,, 5=Not at all bothersome), and 7 (1=A great deal,, 5=Not at all), then subtract the lowest possible score (3) from the raw score and divide by the range of possible scores (15-3=12), then multiply by 100. If less than half of the responses are missing, then the score will be calculated by substituting the missing responses with the average of the non-missing responses, otherwise no score is calculated. If data for an assessment time point are missing, the outcome variable will be coded as missing.				
OAB-SAQ-q Endorsement Score at 3, 6, 9, 12 Months	Continuous	NOTE: The scoring manual for the OAB-SAT-q states that higher scores should correspond to better outcomes and details that final composite scores for each dimension should be obtained by subtracting raw scores from the highest possible score and dividing by range. However, based on the direction of score for individual responses, this derivation would result in lower scores corresponding with better outcomes. We have adjusted the scoring algorithm instead to be: 100*(raw score – lowest possible				

Variable	Туре	Definition					
		score)/score range. This calculation results in higher scores corresponding to better outcomes and an overall scale of 0-100.					

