		The OAB-SAT-q Endorsement Score will be computed at 6 months (and 3, 9, and 12 months) using the standard scoring algorithm. Specifically, instructions are to sum responses across questions 9 (1=Definitely would not use the same treatment again,, 4=Definitely would use the same treatment again), 10 (1=Definitely would not recommend,, 4=Definitely would recommend), and 11 (1=Extremely Dissatisfied,, 6=Extremely Satisfied), then subtract the lowest possible score (3) and divide by the range of possible scores (14-3=11), then multiply by 100. If less than half of the responses are missing, then the score will be calculated by substituting the missing responses with the average of the non-missing responses, otherwise no score is calculated. If data for an assessment time point are missing, the outcome variable will be coded as missing.					
OAB-SAT-q Convenience Score at 3, 6, 9, 12 Months	Continuous	NOTE: The scoring manual for the OAB-SAT-q states that higher scores should correspond to better outcomes and details that final composite scores for each dimension should be obtained by subtracting raw scores from the highest possible score and dividing by range. However, based on the direction of score for individual responses, this derivation would result in lower scores corresponding with better outcomes. We have adjusted the scoring algorithm instead to be: 100*(raw score – lowest possible score)/score range. This calculation results in higher scores corresponding to better outcomes and an overall scale of 0-100.					
		The OAB-SAT-q Convenience Score will be computed at 6 months (and 3, 9, and 12 months) using the standard scoring algorithm. Specifically, instructions are to use the response to question 4 (1=Extremely Inconvenient,, 6=Extremely Convenient), then subtract the lowest possible score (1) and divide by the range of possible scores (6-1=5), then multiply by 100. If the response to question 4 is missing, then no score is calculated. If data for an assessment time point are missing, the outcome variable will be coded as missing.					

Variable	Туре	Definition

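### The OAB-SAT-q Endorsement score fills a blank item with the mean of items scored on different ranges, so a score can reach 109 on a 0-100 scale or be capped at 82

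*SAP*

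**What the plan says.** The Endorsement entry in SAP 9.2 (Variable Definitions) sums three items. Question 9 runs from 1 to 4 ("4=Definitely would use the same treatment again"), question 10 from 1 to 4 ("4=Definitely would recommend"), and question 11 from 1 to 6, the top answer being extreme satisfaction. The sum is then converted: "subtract the lowest possible score (3) and divide by the range of possible scores (14-3=11), then multiply by 100".

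The missing-item rule has a trigger and an action. The trigger is "If less than half of the responses are missing"; the action is that "the score will be calculated by substituting the missing responses with the average of the non-missing responses". If half or more are missing, there is no score.

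A note in the same entry explains that the SAP has changed the direction of scoring given in the instrument's manual, and says of the changed formula: "This calculation results in higher scores corresponding to better outcomes and an overall scale of 0-100". Protocol 3.4.3.a confirms that the instrument mixes 4-, 5- and 6-point response formats.

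**The concern.** Filling a blank with the mean of the other answers is safe only if the items share a range. Here a 4-point item can be filled from a 6-point item, which pushes the filled value above anything the woman could have ticked. A 6-point item can also be filled from two 4-point items, and then it can never reach its own top value. The resulting score may leave the stated scale, and both the sign and the size of the error depend on which question was skipped.

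The affected records would enter the comparison of the Endorsement subscale between arms as valid values. A score above 100 might be noticed. A score that is too low stays inside 0-100 and looks ordinary. The masked data review in SAP 7.6 is directed at the primary, secondary and key outcomes and would not be expected to find it.

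**Working it through.** **Inputs** (all from the Endorsement entry in SAP 9.2): item ranges 1-4, 1-4 and 1-6; lowest sum 3; divisor 11. With three items, fewer than half missing means exactly one blank (1/3). Two blanks (2/3) give no score.

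**The plan's own figure.** The highest sum is 4 + 4 + 6 = 14, and 14 - 3 = 11, as stated. Over all 4 x 4 x 6 = 96 complete response patterns, 100 x (sum - 3)/11 runs from 0 to 100. For complete records the formula is correct.

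**One item blank, both answered items at their maximum.**

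| Blank item | Filled value | Sum | Score |
|---|---|---|---|
| Question 9 or 10 | (4 + 6)/2 = 5, on an item with maximum 4 | 15 | 100 x (15 - 3)/11 = 109.1 |
| Question 11 | (4 + 4)/2 = 4, on an item with maximum 6 | 12 | 100 x (12 - 3)/11 = 81.8 |

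Enumerating every answered pair with each item blank in turn gives the same limits. With question 9 or 10 blank the scores run from 0 to 109.1 (24 pairs, one of them above 100). With question 11 blank they run from 0 to 81.8 (16 pairs). The filled value also exceeds 4 for the pairs 3 and 6, and 4 and 5, where it is 4.5.

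**All other patterns.** Let s be the sum of the two answered items minus 2. The filled value is (s + 2)/2, the total is 1.5(s + 2), and the SAP score is 100 x 1.5s/11 whichever item is blank. Scoring against the ranges of the answered items gives:

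- question 9 or 10 blank: 100 x s/(3 + 5) = 100s/8, so the SAP score is (1.5/11) x 8 = 12/11 of it (+9.1%);
- question 11 blank: 100 x s/(3 + 3) = 100s/6, so the SAP score is (1.5/11) x 6 = 9/11 of it (-18.2%).

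The error therefore affects every non-zero score with one blank, and not only the best responders.

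**A mid-range example.** Answers 3, 3, 5 score 100 x (11 - 3)/11 = 72.7 when complete.

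- Question 9 or 10 blank: the SAP gives 100 x 9/11 = 81.8; range-based scoring gives 100 x 6/8 = 75.0. The rule accounts for +6.8.
- Question 11 blank: the SAP gives 100 x 6/11 = 54.5; range-based scoring gives 100 x 4/6 = 66.7. The rule accounts for -12.1.

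The remaining gap to 72.7 is the ordinary loss from not having the item.

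**Effect on group means.** The documents give no rate of item non-response, so assume 1-5% of records have one blank. The largest single error is 18.2 points, so a group mean moves by at most 1% x 18.2 = 0.2 to 5% x 18.2 = 0.9 points.

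**Other scores.** The Satisfaction items are all 1-6 and the Side Effects items all 1-5. With every answered item at its maximum, the same fill gives (18 - 3)/15 and (15 - 3)/12, both 100. The OAB-q subscale items are all 1-6. The rule does no such harm in those scores.

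**The case against.** The arithmetic is not in dispute; the case against concerns weight.

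- **Exploratory outcome.** OAB-SAT-q is exploratory (SAP 3.2.3) and its p-values are descriptive (SAP 7.8). No primary or secondary conclusion is touched. This stands.
- **The arm difference moves less than a group mean.** If 5% of records in both arms have one blank, unrelated to score, a true difference is multiplied by between 1 - 0.05 x 2/11 = 0.991 and 1 + 0.05 x 1/11 = 1.005, so a 10-point difference moves by at most about 0.09. This stands under those assumptions. If the arms skipped different items, with all scores at the top, the shift could reach 5% x (18.2 + 9.1) = 1.4 points.
- **109 is a corner case.** It needs question 9 or 10 blank and both other answers at maximum; the next highest value is 100 x 1.5 x 7/11 = 95.5. This is true of the breach of 100, but the 12/11 and 9/11 factors apply throughout.
- **The fill may be the instrument's own convention.** The SAP calls its calculation the standard algorithm, and it also averages answered items of unequal range in the PISQ-IR global quality scores. Whether the OAB-SAT-q manual prescribes this fill cannot be settled from the documents. However, the SAP has already departed from that manual where its formula did not give the intended scale, and the same reasoning applies here. The SAP entries for those PISQ-IR scores also state no 0-100 scale for the averaging to break.

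**Conclusion.** The concern holds. Followed as written, the rule gives wrong values: up to 109.1 with question 9 or 10 blank, and never above 81.8 with question 11 blank, on a scale the SAP states as 0-100. Two women who each give the best answer to everything they completed can differ by 109.1 - 81.8 = 27.3 points solely because of which item was skipped.

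The point is minor. It concerns one exploratory subscale and only those records with exactly one of three items blank. Under the assumed 1-5% of such records, the shift in a group mean stays below 1 point. The item-level errors follow from the SAP text alone; only the size of the group effect rests on the assumed rate.

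**What to change.** Replace the missing-item sentence in the Endorsement entry of SAP 9.2 with this rule: if at least two of questions 9, 10 and 11 are answered, the score is 100 x (sum of answered items - number of items answered) / (sum of the ranges of the answered items), the ranges being 3, 3 and 5; otherwise the score is missing.

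With no blank this is 100 x (sum - 3)/11, the formula already written. It keeps the two-of-three threshold and stays within 0-100 for every pattern.

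The cost is one line of SAP wording and one of code. Check the scoring manual at the same time. If it prescribes the raw-mean fill, record this as a second departure beside the one on scoring direction, since it may slightly reduce comparability with earlier uses of the instrument.
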